All abbreviations used throughout the protocol must be defined.

AE	Adverse Event
CFR	Code of Federal Regulations
CRF	Case Report Form
CTSC	Clinical Translational Science Center
DSMB	Data Safety Monitoring Board
DSMP	Data Safety Monitoring Plan
FDA	Food and Drug Administration
GCP	Good Clinical Practice
HIPAA	Health Insurance Portability and Accountability Act of 1996
HRBFA	Human Research Billing Analysis Form
HUD	Humanitarian Use Device
ICF	Informed Consent Form
IDE	Investigational Device Exemption
IND	Investigational New Drug
IRB	Institutional Review Board
PHI	Protected Health Information
PI	Principal Investigator
REDCap	Research Electronic Data Capture
RP	Radical Prostatectomy
SAE	Serious Adverse Event
SBRT	Stereotactic Body Radiotherapy
SUSAR	Suspected Unexpected Serious Adverse Reaction
UAP	Unanticipated Problem
WCM	Weill Cornell Medicine

Protocol Summary

Full Title:	PRE-ProstAtectomy MRI-GuidEd Stereotactic Body RadioTherapy for High-Risk Prostate Cancer Trial
Short Title:	PREPARE SBRT
Clinical Phase:	I
Principal Investigators:	[name] and [name]
Sample Size:	N = 20-40 (3 patients per dose escalation arm with 7 additional patients in maximum tolerated dose arm)
Accrual Ceiling:	This study will enroll up to 45 subjects.
Study Population:	Men with prostate cancer with Gleason Score of 8 or greater or clinical/radiographic evidence of T3 disease
Accrual Period:	3 years
Study Design:	Single arm, feasibility and safety dose escalation study
Study Duration:	Patients will remain on study for 5 years.
Study Agent/	
Intervention Description:	Stereotactic Body Radiotherapy (SBRT)
Primary Objective:	The primary outcome is that a patient can undergo a radical prostatectomy after SBRT without a post-operative dose limiting toxicity (DLT) within 30 days after prostatectomy. DLT will be considered as Grade 3 or higher adverse events according to the Clavien-Dindo Classification
Secondary Objectives:	Secondary objectives include assessment of acute toxicity and quality of life scores.
Exploratory Objectives:	Exploratory objectives will include analysis of tumor and normal biopsied and resected tissue and serum markers and interpretation of interfraction and intrafraction MRIs.
Endpoints:	The primary endpoint is the ability of a patient to undergo a radical prostatectomy without a post-operative Grade 3 or higher adverse events within 30 days according to the Clavien-Dindo Classification

Document History

Document Name	Version number	Version Date
Amendment 7	7.0	09OCT2024
Amendment 6	6.0	10SEP2020
Amendment 5	5.0	26JUN2020
Amendment 4	4.1	18MAR2020
Amendment 3	4.0	10.03.2019
Amendment 2	3.0	06.18.2019
Amendment 1	2.0	10.25.2018
Initial Protocol	1.0	04.24.2018

Summary of changes: Protocol 09OCT2024 version 7.0

1. Removing [name] as PI from the protocol, as he has left WCM.
2. Updating [name] role to be the new PI for the protocol.
3. Removing [name], [name], [name] and [name], as they have left WCM.
4. Adding [name] as Study Contact.
5. Adding [name] and [name] as Responsible Study/Data Manager.
6. Removing personnel will not affect the integrity of the research.

Summary of changes: Protocol 10SEP2020 version 6.0

1. Removing Stool sample collection from the protocol.
2. Updating schema to reflect changes in the study design.

Summary of changes: Protocol 26JUN2020 version 5.0

1. Reducing the dose escalation to include only 3 doses, 5 Gy, 6Gy and 6.5 Gy.
2. Removing [name] from the study as she is no longer with our department.

Summary of changes: Protocol 18MAR2020 version 4.1

1. Adding [name] as a Co-investigator on the study.

Summary of changes: Protocol 10.03.2019 version 4.0

1. Change study title to PREPARE SBRT: PRE-Prostatectomy MRI-Guided Stereotactic Body Radiotherapy for High-Risk Prostate Cancer Trial
2. Modify primary objective and primary end point-- The primary outcome is that a patient can undergo a radical prostatectomy after SBRT without a post-operative Dose limiting toxicity (DLT). DLT will be defined as Grade 3 or higher adverse events within 30 days of prostatectomy according to the Clavien-Dindo Classification.
3. In Secondary end points: added International Prostate Symptom Score (IPSS) instead of EQ5D.

4. Revised stats section 8 and stopping rule section 10.2
5. Removed from Exclusion criteria: Prior chemotherapy and ADT
6. Remove pre-surgery research samples from the Table 1 Study procedures
7. Updated- serum to PBMCs in Section 6 to make it consistent with the initial e IRB application
8. Added [name] as a statistician
9. Remove [name] as a co-investigator.

Summary of changes: Protocol 06.18.2019 version 3.0

1. Removing SPACEOAR™ from the protocol as Augmenix is no longer the sponsor of the study.
2. Adding [name] as an additional data manager for the study
3. Revising phone numbers for [name] and [name]

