escalation and de-escalation study to determine maximum tolerated dose (MTD) and the recommended phase II dose (RP2D) based on acute toxicity measures. Part 2 will be a cohort expansion study to further evaluate the safety and tolerability of the RP2D based on toxicities measured at 1 year.

In part 1 of the study, a modified dose escalation and de-escalation design with an expansion of 3 or 6 patients to allow the recommended phase II dose (RP2D) be examined in a total of 9 patients will be used. The dose limiting toxicity (DLT) is defined as Grade 3 or higher (G3+) gastrointestinal (GI) and/or urinary (GU) AEs related to preoperative radiotherapy according to the Clavien-Dindo Classification at 30 days. Three radiation dose levels, 5 Gy, 6 Gy and 6.5Gy are considered. A 3+3 dose escalation plan will be used. At the start of each dose level k ($k=1, 2$, or 3), 3 patients will be enrolled and treated for five days. If none of the 3 patients develop the DLT, the testing dose will escalate to the next level, $k+1$. If 1 of the 3 patients develops the DLT, the current dose will be tested in an additional 3 patients. If no additional patients develop the DLT, the dose will escalate. If 1 of the additional 3 patients develops DLT, i.e. a total of 2 of 6 patients with DLT, the previous dose will be deemed the maximum tolerated dose (MTD) and tested in a total of 9 patients. If ≤ 2 among the 9 patients experience the DLT, this dose will be considered as the RP2D. If ≥ 2 of 3 patients or ≥ 2 of 6 patients develop DLT, the study will stop without MTD if $k=1$ or consider dose level $k-1$ to be the MTD and tested in an additional 3 or 6 patients so that a total of 9 patients are evaluated. If ≥ 3 of 9 patients experience the DLT, the de-escalation will continue. This design ensures that the DLT rate to be $\leq 2/9$ for the RP2D.

In part 2 of the study, additional 21 patients will be enrolled to further examine the safety of the R2PD in a total of 30 patients. The primary safety endpoint will be G2+ GI and/or GU AEs related to preoperative radiotherapy according to the CTCAE v5.0 measured at 1 year. Patients will be continuously monitored to ensure the acute G3+ GU and/or GI AEs based on the Clavien-Dindo Classification at 30 days do not exceed 4 of 18 patients, and 6 of 27 patients.

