8.2 Sample Size/Accrual Rate

The sample size for part 1 portion of the study will vary depending on the number of patients that develop the DLT. If no DLTs are seen, we will recruit $3+3+3+6=15$ patients at 5, 6, and 6.5 Gy, respectively. Following the schema above, the maximum number recruited would be 27, which would only occur if 0 of 3 or 1 of 6 patients develop the DLT in dose escalation phase but >2 of 6 or >1 of 3 patients in the expansion cohort develop the DLT, triggering an expanded cohort at a lower dose.

Sample size for part 2 portion of the study will be 30 including the 9 patients from part 1. Having a total of 30 patients in the expansion cohort will allow us to estimate the 1-year G2+ toxicity rate based on CTCAE v5.0 within a 95% CI width of 0.37 and help with the decision making at the end of the trial. For example, an observation of ≥ 8 of the 30 patients having G2+ toxicity at 1-year based on CTCAE v5.0 would suggest that the probability of the toxicity rate being > 0.20 is greater than 80%, which will allow us to make an informative decision on whether the R2PD is worth to be examined at a larger trial.

8.3 *Stratification Factors*

No stratification factors are planned for the primary endpoint.

8.4 *Analysis of Endpoints*

8.5 *Analysis of Primary Endpoints*

Primary endpoints for this study are G3+ GU and/or GI toxicities at 30 days based on Clavien-Dindo Classification (Part 1) and G2+ GU and GI toxicities at 1 year based on CTCAE v5.0 (Part 2). Adverse events based on the two classification systems will be recorded. Descriptive statistics including the number, proportion of patients experience AEs, and 95% confidence interval of the proportion estimate calculated using the Clopper-Pearson method will be summarized. The analysis set will include patients who receive any dose of the preoperative radiation therapy.

8.6 *Analysis of Secondary Endpoints*

Assessment and analysis of secondary endpoints including toxicity and quality of life scores will be descriptive.

8.7 *Interim Analysis*

This study will have interim analyses after every dose in the sense that if any unacceptable dose limiting toxicities are seen, future patients will be recruited at a lower dose.

9 *Adverse Event Reporting Requirements*

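### The Protocol Summary's sample size and accrual ceiling are not reconciled with Section 8, whose own maximum is 48 patients against a ceiling of 45

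*Combined protocol and SAP*

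**What the plan says.** The Protocol Summary gives the sample size as "N = 20-40 (3 patients per dose escalation arm with 7 additional patients in maximum tolerated dose arm" and sets the accrual ceiling separately: "This study will enroll up to 45 subjects".

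Section 8.1 sets out a two-part design. For Part 1, "Three radiation dose levels, 5 Gy, 6 Gy and 6.5Gy are considered", each starting with three patients. After one DLT in three, "If 1 of the 3 patients develops the DLT, the current dose will be tested in an additional 3 patients". The dose taken as the MTD is then "tested in an additional 3 or 6 patients so that a total of 9 patients are evaluated", and de-escalation continues if three or more of the nine have a DLT. For Part 2, "additional 21 patients will be enrolled to further examine the safety of the R2PD in a total of 30 patients".

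Section 8.2 puts Part 1 at 15 patients if there are no DLTs and says that "the maximum number recruited would be 27". It confirms that the 30 patients of Part 2 include the 9 from Part 1. Neither the Summary nor Section 8 gives a combined total for the two parts.

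**The concern.** The sample size and the accrual ceiling should both follow from the design in Section 8, and they do not. The ceiling lies below the largest enrolment that the design can call for. The description in the Summary has no 21-patient expansion, which is more than half of the 36 patients needed when no DLTs occur. A reader of the Summary alone would expect a different trial from the one in Section 8.

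Two things are at stake. The approved enrolment limit should cover every path that the design allows. The 30 patients at the RP2D also support the confidence interval width of 0.37 and the worked example of 8 in 30 in Section 8.2, so a ceiling that cuts this group short would undercut the stated justification.

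**Working it through.** **Inputs.** Three dose levels; 3 patients per level, extended to 6 after one DLT in three; 9 at the MTD; de-escalation at 3 or more of 9; 21 more in Part 2 (all Section 8.1). Part 1 size of 15 to 27 (Section 8.2). Range 20–40, 3 per level plus 7 at the MTD, ceiling 45 (Protocol Summary).

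**Reproducing Section 8.2.** With no DLTs, 3 + 3 + 3 + 6 = 15. Following every path of the Section 8.1 rules gives a Part 1 maximum of 9 × 3 = 27. Both figures match.

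**Combined totals.**
- No DLTs: 15 + 21 = 36.
- Maximum: 27 + 21 = 48. This path can be reached with Part 2 still to run. For example: 1 of 6 with a DLT at each level during escalation, then at least 3 of 9 on expansion at the third level and again at the second, then at most 2 of 9 at the first. Part 1 has then used 27 patients and has an RP2D.
- Minimum for a completed trial: 12 + 21 = 33. For example, 3 patients at the first level, at least 2 of 3 with a DLT at the second, and the first level then filled to 9.
- Part 1 sizes that yield an RP2D are 12, 15, 18, 21, 24 and 27, so completed totals are 33, 36, 39, 42, 45 and 48.

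Against the Summary, 48 − 45 = 3 over the ceiling and 48 − 40 = 8 over the range. Totals of 42 and 45 are also above 40.

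**The Summary's recipe.** 3 × 3 + 7 = 16, below its own lower bound of 20. No whole number of levels gives 20, since (20 − 7)/3 = 4.33. At the MTD it gives 3 + 7 = 10, against 9 in Section 8.1 for Part 1 and 30 after Part 2.

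**How often it matters.** The documents give no DLT rates, so three sets are assumed for the three levels. Exact enumeration of the Section 8.1 tree, with independent patients, no replacements, and before the Part 2 stops of Section 10.2:

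| Assumed DLT rates | Total above 40 | Total above 45 |
|---|---|---|
| 5/10/15% | 6.8% | 0.07% |
| 10/20/35% | 16.8% | 0.8% |
| 20/30/40% | 12.8% | 1.0% |

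With the Part 2 stops applied, the chances of passing 40 are 6.6%, 13.8% and 8.0%, and of passing 45 are 0.07%, 0.8% and 0.8%.

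**Effect if the ceiling binds.** On the 48-patient path a ceiling of 45 leaves 45 − 27 = 18 for Part 2, hence 9 + 18 = 27 at the RP2D. The widest 95% Clopper-Pearson interval is 0.374 for n = 30 (15 of 30), which reproduces the 0.37 in Section 8.2, and 0.394 for n = 27 (13 of 27).

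**The case against.** Section 8 states the operative counts clearly: 9 at the MTD, 21 more, 30 in all. The conflict lies in the Summary and the ceiling. Several stronger readings are tempting, and the documents do not support them.

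- *The no-DLT total contradicts the Summary.* It does not: 36 lies inside 20–40 and below 45. Of the completed totals, only 48 breaches the ceiling.
- *A total near 20 is impossible.* No completed trial is that small, but a stopped one can be. A Part 2 stop at 18 patients after a Part 1 of 12 gives 12 + 9 = 21, and Part 1 can end without an RP2D at smaller or similar numbers. What is wrong at the lower end is that the recipe gives 16. Even with every level extended to six it gives only 6 × 3 + 7 = 25, short of 33.
- *There is no room to replace patients who never reach surgery.* Under a ceiling of 45, completed totals of 33, 36, 39 and 42 leave 12, 9, 6 and 3 places. Room runs out only at 45 or 48. Section 8 also states no replacement rule, and Section 8.5 analyses everyone who receives any of the radiotherapy.
- *The trial would lose a safety look or its decision rule.* At 27 patients the last Part 2 look in Section 10.2 has already been reached. The 8 in 30 is offered in Section 8.2 as an example, not a rule. Near that rate the interval widths are 0.336 (8 of 30) and 0.352 (7 of 27), both inside 0.37.

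These points limit the consequences. They do not remove the mismatch: 48 exceeds 45, the recipe does not produce its own range, and the Summary omits Part 2.

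**Conclusion.** The point holds as a failure to reconcile the Summary with Section 8. It needs no assumption to show that the design's maximum of 48 exceeds the ceiling by 3 and the stated range by 8, that the recipe gives 16 patients with 10 at the MTD, and that the 21 Part 2 patients are missing from it. Only the probabilities depend on assumed DLT rates, and they show a rare problem at the ceiling (about 1% or less) and a less rare one at the top of the range (about 7% to 17% before Part 2 stops). The loss of precision if the ceiling binds is small. This is a should-fix correction; a claim that the ceiling endangers the trial's conclusions would go beyond the documents.

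**What to change.** Restate the Summary's sample size from Section 8, along these lines: *N = 36 if no DLTs occur; Part 1 up to 27; 9 patients at the MTD, then 21 more in Part 2 (30 at the RP2D); overall maximum 48, fewer if the trial stops early.* Delete the reference to seven further patients at the MTD. Add the same combined total to Section 8.2.

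Set the accrual ceiling to at least 48, so that it covers the design's own maximum, and put the amended ceiling through IRB review. Keeping 45 by shortening Part 2 to 18 patients is not an equivalent wording correction, because it changes the design and its precision statement.

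The cost is a short amendment to the Summary and Section 8.2, with no change to the dose-finding rules, the Part 2 size or the analysis.

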1.1 Primary Objectives

Assess the feasibility of stereotactic body radiotherapy (SBRT) before radical prostatectomy (RP) in patients with high risk prostate cancer. The primary outcome is that a patient can undergo a radical prostatectomy after SBRT without a post-operative dose limiting toxicity (DLT). DLT will be defined as Grade 3 or higher adverse events within 30 days after prostatectomy according to the Clavien-Dindo Classification.

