5.4 Radiation Treatment Planning

Three (3) patients will initially receive 5 Gy for 5 fractions. If patients tolerate the dose and undergo surgery without a post-operative Grade 3 or higher DLT 30 days, another set of 3 patients are selected for the next dose level. If the patients are to develop a post-operative Grade 3 or higher DLT, the trial will accrue additional 6 patients to the previous dose level.

The treatment planning CT will be fused to the T2 sequence of the MRI. The prostate + seminal vesicles (SV) will be contoured as the clinical target volume (CTV). The PTV expansion for the CTV will be 3-5 mm depending on physician discretion.

The bladder, femoral heads, penile bulb will also be contoured as normal structures.

The CTV (prostate + SV) will be treated to the prescribed dose (5, 6, or 6.5) Gy in 5 fractions.

VPrescription Dose (5, 6, or 6.5) Gy (volume of the PTV receiving Prescription (5, 6, or 6.5) Gy should be $\geq 95\%$)

18

- Gy,
1. Rectum: Maximum dose to 1 cc 38.5 Gy, Max dose to 3 cc 34.4 Gy, D53% 24
Max point dose 40 Gy
 2. Bladder: Maximum dose to 1 cc 38.5 Gy, Max point dose 40 Gy
 3. Penile Bulb: No more than 105% of prescription dose; D3cc 25 Gy. This is a
soft constraint.
 4. Femoral heads: Maximum point dose 30 Gy
 5. Small bowel: Maximum point dose 25 Gy
 6. Urethra: Max dose 38.78 Gy

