All patient data will be entered and maintained in REDCap. These data include clinical data and all patient safety data. The REDCap provides audit trails that track creation and modification of records that include user ID and timestamp. Once entered, the data is subjected to validation procedures that are executed either immediately or upon saving the eCRF page or during the batch validation process. Validation failures that are identified before the page is saved can be corrected immediately. Validation failures during saving of the eCRF page and during batch validation processes will generate a discrepancy. Depending on the database account privileges, the data managers may be able to correct a discrepancy or if not, route it to the project data manager at WCMC who can take appropriate action to correct the problem. Once the discrepancy is closed, by marking “resolved” or “irresolvable”, the data is marked clean and an audit trail is generated by the system.

All key end points will be source verified by a second person at each site and errors will be corrected. Once the data is verified and all discrepancies are closed, the data can be locked/frozen. Locking and freezing can be done at different granular levels and will follow institutional SOPs and any specific requirements for the project.

Security measures that will be taken in order to protect patient data will include firewall technology and database level security which will be achieved by assigning roles and privileges to different levels of users and by requiring that the users authenticate themselves using user id and password. Additional security for data transfer between remote clients and servers will be achieved by using digital certificates/SSL. All data will be backed-up to tape periodically according to the Institutional SOPs. All data will be stored for at least 5 years following the termination of this study.

7.4 *Regulatory Considerations*

All protocol amendments and consent form modifications will be made by the Principal Investigator.

8 *Statistical Considerations*

The primary endpoint for this trial will be successful completion of radical prostatectomy after SBRT without a post-operative DLT of grade 3 or higher within 30 days after prostatectomy.

8.1 *Study Design/Endpoints*

This is a single-arm study including two parts. Part 1 will be a modified dose

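### The declared primary endpoint is not the event that escalation, RP2D selection, stopping and the Section 8.5 primary analysis count

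*Combined protocol and SAP*

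**What the plan says.** The 30-day event is described in several places.

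- **Protocol Summary:** "DLT will be considered as Grade 3 or higher adverse events according to the Clavien-Dindo Classification". The window is 30 days after prostatectomy.
- **Section 1.1:** "DLT will be defined as Grade 3 or higher adverse events within 30 days after prostatectomy according to the Clavien-Dindo Classification". As in the Summary, organ system and cause are not restricted.
- **Section 5.4:** the next cohort opens if patients "undergo surgery without a post-operative Grade 3 or higher DLT 30 days". Nothing is said here about organ system or attribution.
- **Section 8, opening sentence:** the primary endpoint is "successful completion of radical prostatectomy after SBRT without a post-operative DLT of grade 3 or higher within 30 days after prostatectomy". Completing the operation is part of the endpoint.
- **Section 8.1:** for the 3+3 and RP2D rules the DLT is "Grade 3 or higher (G3+) gastrointestinal (GI) and/or urinary (GU) AEs related to preoperative radiotherapy according to the Clavien-Dindo Classification at 30 days". The start of the 30 days is not given.
- **Section 10.2:** the stopping rules use the same organ and attribution limits as Section 8.1 and call the event post-operative.
- **Section 8.5:** "Primary endpoints for this study are G3+ GU and/or GI toxicities at 30 days based on Clavien-Dindo Classification (Part 1". Relatedness and completion of surgery are not mentioned, and the analysis set is everyone who received any preoperative radiation.

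No section says which description governs.

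**The concern.** The stated question is whether prostatectomy is feasible after SBRT. If Sections 8.1, 8.5 and 10.2 are followed exactly, the dose decisions and the primary estimate answer a narrower question, namely how often GI/GU toxicity occurs (in 8.1 and 10.2, only if attributed to radiotherapy).

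Two kinds of failure drop out. One is a serious post-operative complication outside GI/GU, or one attributed to the surgery alone. The other is a patient who is irradiated and never has the operation. Both bear directly on feasibility. At stake is whether the reported Part 1 result is an estimate of the declared primary outcome, and whether two people applying the protocol would reach the same count against the 3, 6, 9, 18 and 27-patient limits.

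**Working it through.** **1. The plan's own figure.** Section 8.2 gives 15 patients for Part 1 if no DLT is seen: 3 + 3 + 3 + 6 = 15. This reproduces. It depends on the DLT count, so what counts as a DLT matters to it.

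**2. Classifying the same patient under each section**

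| Patient | 1.1 / Summary | 8.1 and 10.2 | 8.5 primary endpoint |
|---|---|---|---|
| RT-related Grade 3+ GI/GU event within 30 days after surgery | counts | counts | counts |
| Grade 3+ urinary event attributed to surgery alone | counts | does not count | counts as written |
| Grade 3+ event outside GI/GU | counts | does not count | does not count |
| Irradiated, never operated on, no GI/GU toxicity | no post-operative window; fails the Section 8 endpoint | does not count | in the denominator, no event |

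On a common post-operative window the three event definitions are nested: 8.1 within 8.5 within 1.1.

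**3. The window.** Section 5.1 places surgery less than 4 weeks (28 days) after radiotherapy. If the 30 days in Section 8.1 ran from the end of radiotherapy, an operation near the limit would leave little more than 30 − 28 = 2 post-operative days under observation. An RT-related event before surgery could then count under 8.1 and not under 1.1. Section 10.2's post-operative label points to surgery as the start but does not state it.

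**4. Effect on a reported result (hypothetical).** Take 9 irradiated patients. One is never operated on, one has a Grade 3+ complication outside GI/GU, and none has a GI/GU event. Section 8.5 reports 0/9 events (Clopper-Pearson 95% interval 0% to 34%). The declared endpoint is met by 9 − 1 − 1 = 7 of 9 (40% to 97%).

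**5. Effect on the dose rules.** The documents give no rates, so these are assumptions: RT-related GI/GU events r = 5% to 10%, and other Grade 3+ events o = 5% to 15%, independent of each other.

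- Event rate under 8.1: p = r. Under 1.1: p = 1 − (1 − r)(1 − o).
- With q = 1 − p, P(level fails 3+3) = 1 − [q³ + 3pq² · q³].
- P(at most 2 of 9) = q⁹ + 9pq⁸ + 36p²q⁷.

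For r = o = 10%, the 1.1 rate is 1 − 0.9 × 0.9 = 0.19. Failure under 8.1 is 1 − [0.729 + 0.243 × 0.729] = 0.094. Under 1.1 it is 1 − [0.5314 + 0.3740 × 0.5314] = 0.270.

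| r | o | Rate under 1.1 | Fails 3+3: 8.1 vs 1.1 | At most 2/9: 8.1 vs 1.1 |
|---|---|---|---|---|
| 5% | 5% | 9.75% | 2.7% vs 9.0% | 99.2% vs 95.0% |
| 5% | 10% | 14.5% | 2.7% vs 17.6% | 99.2% vs 87.0% |
| 5% | 15% | 19.25% | 2.7% vs 27.5% | 99.2% vs 75.8% |
| 10% | 5% | 14.5% | 9.4% vs 17.6% | 94.7% vs 87.0% |
| 10% | 10% | 19% | 9.4% vs 27.0% | 94.7% vs 76.4% |
| 10% | 15% | 23.5% | 9.4% vs 36.8% | 94.7% vs 64.3% |

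Independence matters little here. If the two kinds of event never fell in the same patient, the 10%/10% rate would be 20%, with 29.1% failing the 3+3 and 73.8% passing at 2/9.

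**The case against.** A narrow, attributable DLT beside a broader feasibility endpoint is a legitimate phase I design, and the operating rules are consistent with each other. Sections 8.1 and 10.2 agree on organ system and attribution, and their Part 2 limits match (at most 4/18 and 6/27 against stopping at 5/18 and 7/27). Section 5.4 uses the term DLT without offering a rival definition. Section 8.5 does not use the term at all and may be shorthand for 8.1. These points stand. A reader might infer three mutually exclusive definitions, or rules for escalation and stopping that contradict each other on what counts. The text does not support that: the clear conflict is between the declared objective and the statistical rules.

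A reader might also infer that complications outside GI/GU could never influence the trial. That goes too far. Section 9 records AEs regardless of cause, Section 10 has them reviewed at every dose level, and Section 10.2 lets the DSMB recommend modification or termination on any safety concern. Section 8.5 also provides for AEs under both classification systems to be recorded, and for descriptive summaries, which could take in such events. What remains is that they have no place in the formal tallies or the named primary endpoint.

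The defence does not remove the main problem. The broad and narrow events carry the same name, and the broad one is declared primary while Section 8.5 plans no estimate of it combined with completed surgery.

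**Conclusion.** The point holds as a contradiction between the declared primary endpoint and the event that the statistical sections count and analyse. It must be fixed, because carrying out Sections 8.1 and 8.5 to the letter does not yield an estimate of the primary outcome in Sections 1.1 and 8.

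The contradiction is read from the text and needs no assumed rate. Its size does need one. Over the assumed ranges, the chance that a dose level fails the 3+3 is 2.7% to 9.4% under Section 8.1 and 9.0% to 36.8% under Section 1.1. These figures illustrate the sensitivity and do not measure an effect in this trial. Whether Section 8.5 differs from 8.1 on relatedness is less certain, since it may be a loose paraphrase. That it omits completion of prostatectomy is plain. Nothing here shows which DLT definition is clinically right.

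**What to change.** 1. Reconcile the Protocol Summary and Sections 1.1, 5.4, 8 (opening), 8.1, 8.5 and 10.2 so that one DLT definition governs the 3/6/9/18/27 counts. It should state the organ systems, whether attribution is required, when the 30 days start, and how a patient who is not operated on is handled. The investigators decide the content.
2. In Section 8.5, add an estimate of the declared primary endpoint: prostatectomy completed without a DLT as reconciled, among all irradiated patients, with the Clopper-Pearson interval already planned.
3. Whichever definition is chosen, tabulate two counts at each dose level, both within 30 days after surgery: Grade 3+ Clavien-Dindo events of any organ and cause, and RT-related GI/GU Grade 3+ events.

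The cost is protocol and SAP wording and an extra table row per dose level. AEs are already to be recorded regardless of cause and under both classification systems, so no new data collection is needed. The reported rate may look somewhat less favourable.
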